14.0 BIOSTATISTICS

Phase I: The phase I portion of this trial will evaluate 2 dose cohorts including 1 de-escalation cohort (N= minimum 4 and maximum 12) as shown in the table below. Only the dose of Debio 1347 will be de-escalated. There will be no intra-patient dose escalation. 1 cycle = 28 days.

The Dose Limiting Toxicity (DLT) observation period includes Day 1 to Day 28 of Cycle 1, plus the assessments prior to drug administration on Cycle 2, Day1.

Cohort/Dose level	Debio 1347	Fulvestrant
-1	60mg	500mg IM
1 (Starting dose cohort)	80mg	500mg IM

If none or one of the initial 3 patients in dose level 1 has DLT, 3 additional patients will be treated at the same dose level. If 2 or more patients experience DLT at this dose level, then dose level -1 will be evaluated. Should 2 or more patients experience DLT at dose level -1, the study will stop accrual. If only 1 of the 3 initial patients experiences a DLT at dose level -1, 3 additional patients will be evaluated at this dose level. Patients who withdraw before completing a full cycle of treatment for reasons other than development of a DLT will be replaced.

Selected non-hematologic and hematologic toxicities, as measured by the NCI CTCAE Version 4.0, will be described by frequency and grade, by cycle and over all cycles, with the maximum grade over all cycles used as the summary measure per patient. In a descriptive secondary analysis, clinical benefit rate will be estimated by dose.

We anticipate accruing 1-2 patients/month in the phase 1b portion of the study.

Phase II: The purpose of the phase II portion of the study is to evaluate the efficacy of this regimen, using the MTD/RP2D as determined in the Phase Ib part of the trial. Efficacy will be measured by the clinical benefit rate: proportion of patients who have a best overall response

of a complete response, a partial response, or stable disease (SD) for at least 24 weeks (SD \geq 24 weeks) i.e. (CR+PR+SD \geq 24 weeks). In the PALOMA-3 trial where ER+ MBC patients were randomized to fulvestrant plus palbociclib versus fulvestrant, the CBR (ORR + SD $>$ 24 weeks) was 34% (95% CI, 29.0 to 39.3) vs 19% (95% CI, 13.4 to 25.6). There is no historic data available for patients who have progressed on palbociclib. Since this trial will allow patients who have received prior palbociclib, it was decided that a target clinical benefit rate below 10% will not be worthy of further consideration and a response rate of 25% will be considered promising.

Simon's two-stage optimal design will be used to study the treatment efficacy since it permits early termination of the study. We will allow early termination only if the data at the first stage indicate that the treatment is highly inactive. 18 patients will initially enter the study. If there are 2 or fewer patients with clinical benefit (CR, PR or SD \geq 24) observed, the study will be terminated early and declared to have a negative result. If 3 or more patients have clinical benefit, enrollment will be extended to 43 patients. Note, we will halt the trial after the first stage while awaiting results from the first 18 patients.

If 8 or more patients with clinical benefit are observed among the 43 patients, the study will be considered to have a positive result and this regimen would be considered worthy of further testing in this disease. The probability of early termination is 0.73 if the true clinical benefit probability is \leq 10%. This design would effectively discriminate between true clinical benefit rates of \leq 10% and \geq 25%. This design has 80% power and a type I error of 5%.

Upon completion of the study, the true clinical benefit rate will be estimated via the observed rate and an exact confidence interval will be constructed.

The maximum of 43 patients requires about 2 years of patient accrual with an anticipated enrollment of 1-2 patients per month.

In secondary analyses for the Phase Ib portion of the trial, the ORR will be summarized as a proportion with a 95% exact confidence interval. TTP, PFS and OS will be evaluated using Kaplan-Meier methods. All toxicities as measured by the NCI CTCAE Version 4.0, will be described by frequency and grade, by cycle and over all cycles, with the maximum grade over all cycles used as the summary measure per patient. All patients will be included in the safety analyses regardless of whether a patient is not evaluable for the efficacy endpoint.

All exploratory analyses will be conducted for each phase of the trial separately. PK/PD measures such as AUC, Cmax, and Cmin will be calculated and summarized. Exploratory endpoints that aim to investigate biomarkers of clinical benefit and/or resistance will be evaluated descriptively and graphically. If there are a sufficient number of clinical benefit events, nonparametric tests (Fisher's exact or Wilcoxon rank sum) will be used to test the exploratory hypotheses depending on the distribution of the biomarker.

Deaths will be censored for the TTP endpoint in secondary analyses. However, we will also evaluate PFS which treated deaths and progression as events. These are secondary

analyses, and if there are a sufficient number of events and types of events, we can consider other approaches, such as the calculation of cumulative incidence functions.

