2.1 OBJECTIVES AND SCIENTIFIC AIMS

Primary Objectives:

Phase 1:

- To determine the safety, tolerability, maximum tolerated dose (MTD)/recommended phase 2 dose (RP2D) of Debio 1347 Plus Fulvestrant in patients with ER+/HER2-/FGFR amplified metastatic breast cancer

Phase 2:

- To investigate the anti-tumor activity of Debio 1347 in combination with fulvestrant in patients with ER+/HER2-/FGFR-amplified metastatic breast cancer as defined as clinical benefit rate (CBR: Objective Response Rate plus Stable disease \geq 24 weeks)

Secondary objectives:

Phase 1:

- To obtain a preliminary assessment of the anti-tumor activity (CBR and overall response rate (ORR)) of Debio 1347 in combination with fulvestrant in patients with ER+/HER2-/FGFR-amplified metastatic breast cancer

Phase 2:

- To further characterize the safety and tolerability of Debio 1347 in combination with fulvestrant in patients with ER+/HER2-/FGFR- amplified metastatic breast cancer
- To determine the overall response rate (ORR), time to progression (TTP), progression-free survival (PFS) and overall survival (OS) for the combination of Debio 1347 with fulvestrant in patients with ER+/HER2-/FGFR- amplified metastatic breast cancer

Exploratory Objectives:

Phase 1 and Phase 2:

- To measure the pharmacokinetic (PK) parameters of Debio 1347 in combination with fulvestrant
- To measure pharmacodynamic biomarkers of FGFR inhibition
- To make an assessment of biomarkers of response and/or resistance from archival tissue and fresh tumor biopsies (using next generation sequencing, FISH, protein and mRNA expression) and plasma (cell-free DNA) and correlate with clinical benefit

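### Should the Phase II clinical benefit interval have a stated level and a two-stage method, so that it agrees with the 8-of-43 rule?

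*Combined protocol and SAP*

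**What the plan says.** Section 14.0 sets up Phase II with "Simon's two-stage optimal design will be used to study the treatment efficacy since it permits early termination of the study". The benchmarks are that "a target clinical benefit rate below 10% will not be worthy of further consideration and a response rate of 25% will be considered promising". The trial stops at 2 or fewer patients with clinical benefit among the first 18 and otherwise goes on to 43. Then "If 8 or more patients with clinical benefit are observed among the 43 patients, the study will be considered to have a positive result". The section states 80% power, a 5% type I error, and a 0.73 probability of stopping early when the true rate is 10% or less.

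Estimation comes in a separate sentence: "the true clinical benefit rate will be estimated via the observed rate and an exact confidence interval will be constructed". No level is given and no allowance for the first-stage stop is mentioned. A level appears once for a planned analysis, where "the ORR will be summarized as a proportion with a 95% exact confidence interval". That paragraph is labelled as Phase Ib, but it goes on to time to progression, progression-free survival and overall survival, which Section 2.1 lists as Phase 2 objectives only. The label may be a clerical slip, in which case 95% may be meant for Phase II too.

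**The concern.** The decision rule allows for the futility stop; an interval computed as if 43 patients had been enrolled in one stage does not. Ignoring the stop, the chance of 8 or more successes in 43 at a true rate of 10% is above 5%, so the ordinary exact 90% interval, whose lower limit carries a one-sided 5% error, falls just below 10% at 8/43. The report would then call the regimen worth further testing beside an interval that still contains the rate judged not worth pursuing. With neither level nor method fixed, someone could also choose them after seeing the count, and at 8/43 that choice settles whether 10% is excluded. At stake is the consistency of the primary-endpoint report, not the go/no-go decision.

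**Working it through.** **Inputs (Section 14.0):** null rate 10%, target 25%, first stage 18 patients, stop at 2 or fewer, total 43 (so 25 in the second stage), positive at 8 or more. X1 is the first-stage count and T the total.

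**1. The plan's own figures.**
- P(stop | p) = P(X1 ≤ 2; 18, p). At p = 0.10 this is 0.734 (stated 0.73).
- P(positive | p) = Σ over x = 3..18 of Bin(x; 18, p) × P(X2 ≥ 8 − x; 25, p). At p = 0.10 this is 0.0480 (stated 5%); at p = 0.25 it is 0.8003 (stated 80%).

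The design is as described.

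**2. Source of the mismatch.** Ignoring the stop, P(X ≥ 8; 43, 0.10) = 0.0607, against 0.0480 with it. One is above 5% and the other below.

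**3. Intervals at 8/43 = 18.6%.** The ordinary exact (Clopper-Pearson) limits solve P(X ≥ 8; 43, pL) = α/2 and P(X ≤ 8; 43, pU) = α/2. The stagewise limits solve P(X1 ≥ 3 and T ≥ 8; pL) = α/2 and 1 − P(X1 ≥ 3 and T ≥ 9; pU) = α/2.

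| Method | 90% | 95% |
|---|---|---|
| Ordinary exact | 9.6% to 31.1% | 8.4% to 33.4% |
| Stagewise exact | 10.1% to 33.3% | 8.8% to 36.3% |

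Only the 90% stagewise interval excludes 10%. At 95% both methods include it, because a two-sided 95% interval is being set against a one-sided 5% rule. At 9/43 the ordinary lower limits are 11.4% (90%) and 10.04% (95%), so 8/43 is the only positive total affected.

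**4. How often 8/43 occurs.** P(X1 ≥ 3 and T = 8) is 2.7%, 11.2% and 7.0% at true rates of 10%, 20% and 25%.

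**5. Whether the ordinary interval is valid.** Use x/18 after a stop and x/43 otherwise, and sum the two-stage probabilities of the outcomes whose interval contains the true rate, for rates from 2% to 60%.
- 95% interval: minimum coverage 94.5%.
- 90% interval: minimum 86.9%, at a true rate of 31.1%; below 90% only at about 31% to 32%. The shortfall is in the upper limit: 8.2% missed against a nominal 5%, of which 4.9% comes from stage-1 stops and 3.3% from totals of 3 to 8.
- The lower limit of the 90% interval, the one compared with 10%, misses at most its nominal 5% anywhere in the range.

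**6. Price of the stagewise interval.** It ranks every continued trial above every stopped one, so low final totals inherit roughly the upper limit of 2/18 (31.0%). The 90% upper limits are:

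| Total | Ordinary | Stagewise |
|---|---|---|
| 3/43 | 17.1% | 31.0% |
| 4/43 | 20.0% | 31.0% |
| 5/43 | 22.9% | 31.1% |

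At these totals the ordinary interval excludes the promising rate of 25% and the stagewise one does not. Their combined probability at a true 10% is 11.1%, about four times that of 8/43 (11.1 / 2.7 ≈ 4.1).

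**The case for a change.** The best case for acting is that this is the primary endpoint, that one or two sentences would settle the matter, and that a two-sided 90% stagewise interval agrees with the count rule at the boundary: its lower limit is 8.6% at 7/43, 10.1% at 8/43 and 11.7% at 9/43. It also keeps coverage at or above 90.1%, where the ordinary 90% interval dips to 86.9%. Fixing level and method in advance would remove any choice made after the result is known.

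The omission is real, and that much stands. The rest carries less weight. The 90% level is not in the plan; it has to be brought in before the method makes any difference at 8/43. The coverage dip belongs to that imported level, lies above both design rates, and concerns the upper limit only. The plan's sentence does not rule out a two-stage exact interval, so silence on method is not a wrong method. Nor can a late choice of interval alter the declared result, because the threshold is a count. Finally, the remedy has its own awkward outcome: at 3/43, observed 7.0%, the 90% stagewise interval runs from 4.7% to 31.0%. A statistician could reasonably prefer the ordinary interval.

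**Conclusion.** No change to the plan is needed. The missing level and method are a detail that analysts would fill sensibly, most naturally with an ordinary exact 95% interval, which is close to nominal in this design (minimum coverage 94.5%). The interval serves estimation; the count of 8 or more decides, with type I error 0.048 and power 0.800. The disagreement at 8/43 is confined to one total. At 95% it merely reflects one-sided testing beside two-sided estimation, and the two-stage method would not remove it. Making interval and rule agree means choosing 90% and stagewise ordering together, and the wider upper limits at 3 to 5 of 43 make that a matter of preference rather than a correction.

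This rests on exactly 18 and 43 evaluable patients, on reading an exact interval as Clopper-Pearson, and on x/18 being used after a first-stage stop.

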15.1 RESEARCH PARTICIPANT REGISTRATION AND RANDOMIZATION PROCEDURES

15.2 Research Participant Registration

Confirm eligibility as defined in the section entitled Inclusion/Exclusion Criteria. Obtain informed consent, by following procedures defined in section entitled Informed Consent Procedures. During the registration process registering individuals will be required to complete a protocol specific Eligibility Checklist. The individual signing the Eligibility Checklist is confirming whether or not the participant is eligible to enroll in the study. Study staff are responsible for ensuring that all institutional requirements necessary to enroll a participant to the study have been completed. See related Clinical Research Policy and Procedure #401 (Protocol Participant Registration).

15.3 Randomization

If the research study requires randomization procedures, this section should be referenced by the Biostatistics section (14.0). Describe in detail the process of randomization, when it should occur, how it is being conducted and who is responsible for carrying it out.

16.1 DATA MANAGEMENT ISSUES

A MSKCC Research Study Assistant (RSA) and Research Project Coordinator (RPC) will assist the PI, [name] with the oversight and conduct of this study. The RSA will be responsible for protocol compliance, data collection, data reporting, AE tracking and reporting, SAE reporting, regulatory submissions, and for coordinating all study participant research activities. The RPC will be responsible for regulatory compliance, overall project compliance, data quality assurance, SAE review, and Medidata database management. Both the RSA and RPC will report to and regularly meet with the PI to review study, data and enrollment status; protocol aberrations, regulatory requirements and any participant toxicities on study.

16.2 Quality Assurance

Throughout the life of the study, the study team comprising of the PI, research fellows, research nurses, RSA, and RPC will meet regularly. During these meetings, they will address accrual rates, review adverse events, and discuss any challenges with using the device in this population. Regular registration reports will be generated to monitor patient accruals and completeness of data. Routine data quality reports will be generated to assess missing data and inconsistencies. Accrual rates and accuracy of evaluations and follow-up will be monitored periodically throughout the study and potential problems will be brought to the attention of the PI and CRM for discussion and action.

Random sample data quality audits will be performed by the RPC and evaluated at the study team meetings.

16.3 Data and Safety Monitoring

The Data and Safety Monitoring (DSM) Plans at Memorial Sloan Kettering Cancer Center were approved by the National Cancer Institute in September 2001. The plans address the new policies set forth by the NCI in the document entitled "Policy of the National Cancer Institute for Data and Safety Monitoring of Clinical Trials" which can be found at: <http://cancertrials.nci.nih.gov/researchers/dsm/index.html>. The DSM Plans at MSKCC were established and are monitored by the Office of Clinical Research. The MSKCC Data and Safety Monitoring Plans can be found on the MSKCC Intranet at: <http://mskweb2.mskcc.org/irb/index.htm>

There are several different mechanisms by which clinical trials are monitored for data, safety and quality. There are institutional processes in place for quality assurance (e.g., protocol monitoring, compliance and data verification audits, therapeutic response, and staff education on clinical research QA) and departmental procedures for quality control, plus there are two institutional committees that are responsible for monitoring the activities of our clinical trials programs. The committees: *Data and Safety Monitoring Committee (DSMC)* for Phase I and II clinical trials, and the *Data and Safety Monitoring Board (DSMB)* for Phase III clinical trials, report to the Center's Research Council and Institutional Review Board.

During the protocol development and review process, each protocol will be assessed for its level of risk and degree of monitoring required. Every type of protocol (e.g., NIH sponsored, in-house sponsored, industrial sponsored, NCI cooperative group, etc.) will be addressed and the monitoring procedures will be established at the time of protocol activation.

17.1 PROTECTION OF HUMAN SUBJECTS

Participants will be informed that information collected during their participation in this study is considered confidential. All data gathered will be kept in a secured location and available only to members of the research study team. Findings will be presented in aggregate form only - with no references made to the individual participant's data. Confidentiality of each participant's data will be protected with utmost care; data will be identified solely by a code number. A list matching participant's names and code numbers will be maintained on a secure and password protected database in MSKCC servers. Participation in this study is entirely voluntary. All participants will be required to sign a statement of informed consent that adheres to MSKCC guidelines. Should a patient decide not to participate in this study or to withdraw their consent to participate at any time during the study, their treatment at MSKCC or participating institutions will in no way be compromised.

17.2 Privacy

MSKCC's Privacy Office may allow the use and disclosure of protected health information pursuant to a completed and signed Research Authorization form. The use and disclosure of protected health information will be limited to the individuals described in the Research Authorization form. A Research Authorization form must be completed by the Principal Investigator and approved by the IRB and Privacy Board (IRB/PB).

The consent indicates that individualized de identified information collected for the purposes of this study may be shared with other qualified researchers. Only researchers who have received approval from MSK will be allowed to access this information which will not include protected health information, such as the participant's name, except for dates. It is also stated in the Research Authorization that their research data may be shared with other qualified researchers.

17.3 Serious Adverse Event (SAE) Reporting

An adverse event is considered serious if it results in ANY of the following outcomes:

- Death
- A life-threatening adverse event
- An adverse event that results in inpatient hospitalization or prolongation of existing hospitalization
- A persistent or significant incapacity or substantial disruption of the ability to conduct normal life functions
- A congenital anomaly/birth defect
- Important Medical Events (IME) that may not result in death, be life threatening, or require hospitalization may be considered serious when, based upon medical judgment, they may jeopardize the patient or subject and may require medical or surgical intervention to prevent one of the outcomes listed in this definition

Note: Hospital admission for a planned procedure/disease treatment is not considered an SAE.

SAE reporting is required as soon as the participant starts investigational treatment/intervention. SAE reporting is required for 30-days after the participant's last investigational treatment/intervention. Any event that occur after the 30-day period that is unexpected and at least possibly related to protocol treatment must be reported.

Please note: Any SAE that occurs prior to the start of investigational treatment/intervention and is related to a screening test or procedure (i.e., a screening biopsy) must be reported.

All SAEs must be submitted in PIMS. If an SAE requires submission to the HRPP office per IRB SOP RR-408 'Reporting of Serious Adverse Events', the SAE report must be submitted within 5 calendar days of the event. All other SAEs must be submitted within 30 calendar days of the event.

The report should contain the following information:

- The date the adverse event occurred
- The adverse event
- The grade of the event
- Relationship of the adverse event to the treatment(s)
- If the AE was expected
- Detailed text that includes the following

- An explanation of how the AE was handled
- A description of the participant's condition
- Indication if the participant remains on the study
- If an amendment will need to be made to the protocol and/or consent form
- If the SAE is an Unanticipated Problem

17.3.1 SAE Reporting to Debiopharm International S.A.

All SAEs, irrespective of their cause, that occur between signature of informed consent and 30 days after the last IMP administration, have to be reported by the Institution to Debiopharm International SA within 24 hours after being informed of their occurrence.

- Serious AEs will be reported to Debiopharm by FAX, e-mail, or phone.
- When reported by FAX, SAEs will be transmitted via the "Serious Adverse Event Report transmittal form" to:

Debiopharm International SA

Fax: [name]

- When reported by e-mail, SAEs will be transmitted to:
- [contact]
- When reported by phone, SAEs will be notified to the Pharmacovigilance Manager of Debiopharm International SA as specified in the site study file.
- All SAEs shall be promptly confirmed in writing at the latest within 3 days of being informed using the "Serious Adverse Event Report transmittal form" of Debiopharm International SA

17.2.1

18.0 INFORMED CONSENT PROCEDURES

Before protocol-specified procedures are carried out, consenting professionals will explain full details of the protocol and study procedures as well as the risks involved to participants prior to their inclusion in the study. Participants will also be informed that they are free to withdraw from the study at any time. All participants must sign an IRB/PB-approved consent form indicating their consent to participate. This consent form meets the requirements of the Code of Federal Regulations and the Institutional Review Board/Privacy Board of this Center. The consent form will include the following:

1. The nature and objectives, potential risks and benefits of the intended study.
2. The length of study and the likely follow-up required.
3. Alternatives to the proposed study. (This will include available standard and investigational therapies. In addition, patients will be offered an option of supportive care for therapeutic studies.)
4. The name of the investigator(s) responsible for the protocol.

5. The right of the participant to accept or refuse study interventions/interactions and to withdraw from participation at any time.

Before any protocol-specific procedures can be carried out, the consenting professional will fully explain the aspects of patient privacy concerning research specific information. In addition to signing the IRB Informed Consent, all patients must agree to the Research Authorization component of the informed consent form.

Each participant and consenting professional will sign the consent form. The participant must receive a copy of the signed informed consent form.

